10. SAFETY

10.1 Drug Studies

During the entire duration of the study, all adverse events (AE) and all serious **adverse** events (SAEs) are collected, fully investigated and documented in source documents and case report forms (CRF). SAEs are to be documented on the Pharming SAE form and reported to PV within 24 hours of awareness. Study duration encompassed the time from when the participant signs the informed consent until the last protocol-specific procedure has been completed, including a safety follow-up period.

As the frequency of comorbidities in the patient population under study is significant and clinical complications are common in patients with COVID-19 infection, serious adverse events are possible in this setting. Hence, the Sponsor will establish periodic interim safety review meetings by an independent committee (see also [Section 1.3](#)).

10.1.1 Definition and Assessment of (Serious) Adverse Events and Other Safety Related Events

An **Adverse Event (AE)** is any untoward medical occurrence in a patient or a clinical investigation participant administered a pharmaceutical product, and which does not necessarily have a causal relationship with the study procedure. An AE can therefore be any unfavorable and unintended sign (including an abnormal laboratory finding), symptom, or disease temporally associated with the use of a medicinal (investigational) product, whether or not related to the medicinal (investigational) product. [ICH E6 1.2]. Any medical conditions

present before signing the informed consent will be reported in the medical history. Any AEs that occur between screening and first treatment are considered as Non-Treatment Emergent Adverse Events (TEAE).

A Serious Adverse Event (SAE) is classified as any untoward medical occurrence that:

- results in death,
- is life-threatening,
- requires in-patient hospitalization or prolongation of existing hospitalization,
- results in persistent or significant disability/incapacity, or
- is a congenital anomaly/birth defect.

In addition, important medical events that may not be immediately life-threatening or result in death, or require hospitalization, but may jeopardize the patient or may require intervention to prevent one of the other outcomes listed above should also usually be considered serious. [ICH E2A]. The EMA Important Medical Events (IME) list will be used as a reference for this.

An elective or pre-planned hospital admission will not be considered as a SAE.

Note: an AE or adverse drug reaction is considered “life-threatening” if, in view of either the Investigator or Sponsor, its occurrence places the patient at immediate risk of death. It does not include an event that, had it occurred in a more severe form, might have caused death. SAEs should be followed until resolution or stabilization. Participants with ongoing SAEs at study termination (including safety visit) will be further followed up until recovery or until stabilization of the disease after termination.

Regardless of the assumed causal relationship, all AE volunteered by the trial subjects or observed by the Investigator and/or his staff must be recorded on the AE forms. Records of AEs include patient data, description of the event, intensity, severity, relationship to the study drugs, temporal relation to the study drugs, action taken, description of outcome and documentation of the results of diagnostic and therapeutic measures.

Assessment of Causality

Both Investigator and Sponsor make a causality assessment of the event to the study drug, based on the criteria listed in the ICH E2A guidelines:

Relationship	Description
Definitely	Temporal relationship Improvement after dechallenge* Recurrence after rechallenge (or other proof of drug cause)
Probably	Temporal relationship Improvement after dechallenge No other cause evident
Possibly	Temporal relationship Other cause possible
Not related	Causal relationship can be ruled out

*Improvement after dechallenge only taken into consideration, if applicable to reaction

Unexpected Adverse Drug Reaction

An “unexpected” adverse drug reaction is an adverse reaction, the nature or severity of which is not consistent with the applicable product information (e.g. Investigator’s Brochure for drugs that are not yet approved and Product Information for approved drugs, respectively). [ICH E2A]

Suspected Unexpected Serious Adverse Reactions (SUSARs)

Adverse reactions are all untoward and unintended responses to an IMP related to any dose administered.

Unexpected adverse reactions are suspected unexpected serious adverse reactions (SUSARs) if the following 3 conditions are met:

1. The event must be serious.
2. There must be a certain degree of probability that the event is a harmful and an unintended reaction to the IMP, regardless of the administered dose.
3. The adverse reaction must be unexpected, that is to say, the nature and severity of the adverse reaction are not in agreement with the product information as recorded in the Investigator's Brochure.

The Investigator and the Sponsor evaluate any SAE that has been reported regarding seriousness, causality and expectedness. If the event is assessed as related, either by the Investigator or the Sponsor, and is considered serious and unexpected, it is classified as a SUSAR.

Assessment of Severity

The Investigator will be required to assess the intensity of the AE and to record this assessment in the source documents. It is important to distinguish between serious criteria and severity of an AE. Severity is a measure of intensity whereas seriousness is determined by the criteria mentioned above. Investigators will use the following categories to quantify severity.

- Mild/grade 1: events require minimal or no treatment and do not interfere with the patient's daily activities.
- Moderate/grade 2: events result in a low level of inconvenience or concern with the therapeutic measures. Moderate events may cause some interference with functioning.
- Severe/grade 3: events interrupt a patient's usual daily activity and may require systemic drug therapy or other treatment. Severe adverse events are usually incapacitating.
- Life threatening/grade 4: potentially life-threatening or disabling. High-risk medical interventions.
- Fatal/grade 5: patient died.

Changes in the severity of an AE will be documented to allow an assessment of the duration of the event at each level of intensity to be performed. AEs characterized as intermittent require documentation of onset and duration of each episode.

10.1.2 Reporting of Serious Adverse Events (SAE) and Other Safety Related Events

Reporting of SAEs

All SAEs must be reported immediately and within a maximum of 24 hours to the Sponsor via email at [contact] or fax at 1 [contact].

Reporting of SUSARs

Fatal or life-threatening SUSARs need to be reported to the IRB and to Competent Authorities (e.g. FDA and EMA) within 7 calendar days. Follow-up information to Fatal or life-threatening SUSARs or other SUSARs need to be reported within 15 calendar days.

The Sponsor must inform all Investigators participating in the clinical study of the occurrence of a SUSAR.

Reporting and Handling of Pregnancies

In case a patient becomes pregnant during the study, the patient should be withdrawn immediately from the study. Any pregnancy during the treatment phase of the study and within 30 days after discontinuation of study medication will be reported to the Sponsor and within a maximum of 24 hours to the Sponsor. The course and outcome of the pregnancy should be followed up carefully, and any abnormal outcome regarding the mother or the child should be documented and reported to the Sponsor following the SAE reporting timelines.

Reporting of Special Situations

All special situations must be reported as an SAE within 24 hours of the Investigator's first knowledge of the event, even if considered non-serious and regardless or not of whether an (S)AE occurred.

Special situations may include, but are not limited to, the following:

- Use of a medicinal product during pregnancy or breastfeeding
- Use of a medicinal product in a pediatric or elderly population
- Reports of overdose, abuse, off-label use, misuse, medication error or occupational exposure
- Lack of therapeutic efficacy
- (Suspected) transmission of an infectious agent

Overdose

For this study any dose of rhC1INH greater than 100 U/kg will be considered an overdose.

Medication errors

A medication error is any unintentional error in the prescribing, dispensing, or administration of a medicinal product while in the control of the healthcare professional or patient. Examples of medication error include, but are not limited to: wrong dose, wrong or inadequate (route of) administration, equipment failure, preparation error. Medication errors are reported in the CRF. A description of the error must be provided and whether or not the medication error lead to any AE.

Periodic Reporting of Safety

In addition to the expedited reporting of SUSARs, the Sponsor will submit, once a year throughout the development program of the IMP, a developmental safety update report (DSUR) to the competent authorities (FDA and EMA) and IRBs, as appropriate.

This safety report consists of:

- A list of all suspected (unexpected or expected) serious adverse reactions, along with an aggregated summary table of all reported serious adverse reactions, ordered by organ system, per study.
- A report concerning the safety of the patients, consisting of a complete safety analysis and an evaluation of the balance between the efficacy and the harmfulness of the medicine under investigation.

10.1.3 Follow up of (Serious) Adverse Events

Participants with SAEs (whether or not related to the study drug) will be monitored until resolution or until the event is considered chronic and/or stable by the Investigator and/or other physician who has the responsibility for the subject's medical care. Treating physicians including general practitioners will be contacted for follow-up results. If necessary, participants will be contacted directly for follow-up. Follow-up SAE reports will be reported according to the same timelines as initial reports. The outcome of AEs will be documented.

10.1.4 Ongoing Safety Monitoring and Stopping Rules

Adverse events and abnormal lab values will be graded using the Common Terminology Criteria for Adverse Events (CTCAE) Version 5.0. A subject who experiences a treatment-emergent anaphylactic/anaphylactoid reaction or thrombotic/thrombo-embolic event will not be permitted to receive further treatment with study drug until the review of the case, discussion with the treating Investigator and Pharming, and further evaluation as required is completed.

Further enrollment into the study, and further rhC1INH administration in all subjects, will be temporarily halted pending a review of the data if either of the following occur:

- If one or more subjects experience a Grade 4 or Grade 5 adverse event possibly related to study drug administration, as assessed by the Investigator or Pharming, or
- If two or more subjects experience a Grade 3 adverse event possibly related to study drug administration.

11. STATISTICAL METHODS

11.1 Hypothesis

Null hypothesis: Early administration of rhC1INH in addition to SOC is not associated with an improved clinical outcome in admitted COVID-19 patients as reflected by a lower score on the WHO Ordinal Scale on day 7 compared to SOC alone.

Alternative hypothesis: Early administration of rhC1INH in addition to SOC is associated with an improved clinical outcome in admitted COVID-19 patients as reflected by a lower score on the WHO Ordinal Scale on day 7 compared to SOC alone.

11.2 Determination of Sample Size

This is a pilot study investigating the efficacy and safety of rhC1INH in the prevention of clinical deterioration in a high-risk population with COVID-19. There is no reliable information available on the clinical evolution of the population included in the trial. Therefore, a precise quantitative pre-definition of the sample size of a population needed to obtain clinically significant primary endpoint is not possible at this point in time.

The assumptions which are proposed and the criteria to monitor and assess the primary endpoint are as follows:

The primary endpoint is a 7-point scale and the standard deviation σ can be expected as 1.5 points. A relevant effect δ is an advantage of at least 1 point. Then, the standardized difference is about $\delta/\sigma = 0.67$. For a fixed sample size design with a two-sided significance level of $\alpha = 0.05$ and a power of $1 - \beta = 0.80$, a sample size of $N = 2 \times 38$ is necessary. Because of a nonparametric test, we add 4 patients in each group, and because of drop-outs we add also 4 patients in each group to $N = 2 \times 46$. For a 2:1-randomization, a nonparametric analysis by the stratified Wilcoxon rank-test, and an adaptive group sequential analysis, the overall sample size is estimated as $120 = 80 + 40$.

All patients are hospitalized, and it is very unlikely that the primary endpoint at Day 7 will not be measured. Nevertheless, a drop-out rate of about 10% is included.

Adaptive Design:

Two interim analyses after 32 and 80 patients are planned according to the Pocock adjusted levels $qp = 0.0221$. Based on the results of an interim analysis the sample size can be adjusted (Lehmacher, Wassmer, 1999). There are no prespecified futility margins, but the DSMB can recommend stopping the study in the case of insufficient interim results.

The primary efficacy endpoint and the main secondary efficacy endpoints will be analyzed at latest at 14 days after start of treatment.

11.3 Statistical Criteria of Termination of Trial

There are no prespecified futility margins, but the DSMB can recommend stopping the study in the case of insufficient interim results.

11.4 Planned Analyses

11.4.1 Datasets to be Analysed, Analysis Populations

A review of the database will be conducted in a blinded manner shortly before the database will be locked, and any decisions made at that meeting (blinded Data Review Meeting) concerning the statistical analysis, e.g., additional outcomes and populations, pooling of sites for efficacy analysis, will be documented in the Statistical Analysis Plan (SAP).

Missing data for the primary endpoint will be imputed by means of the Last-observation-carried-forward (LOCF) method, as sensitivity analyses some alternative imputation methods like imputation of the mean and multiple imputation will be additionally performed.

Safety Population: The Safety Population is defined as all patients who received at least one dose of rhC1INH. Statistical analyses will be based on the actual treatment the patient received.

Full Analysis Set/Intent-to-Treat Population: The FAS/ITT Population is defined as all patients who are randomly allocated to a study arm. Statistical analyses will be based on the treatment arm to which the patient was allocated. For quantitative data, the number of patients with non-missing information, means, medians, standard deviations and extremes will be determined. For qualitative data, absolute and relative frequencies will be calculated. Moreover, changes from baseline (V2, d0) will be calculated.

Per Protocol Population: The PP Population is defined as all patients in the FAS/ITT Population who complete the study and who do not have any major protocol violations, including the following:

- Patients who had major inclusion/exclusion criteria violations.

Sufficient compliance is expected because of IV administration of the IMP.

The PP Population will be determined by a blinded review in the Data Review Meeting (DRM) of the data prior to database lock. The primary efficacy analysis will be based on the FAS/ITT Population in this superiority trial; an additional efficacy analysis will be performed on the PP Population. The Safety Population will be used for all safety analyses.

11.4.2 Primary Analysis

The primary endpoint WHO Ordinal Scale measure at day 7 will be analyzed by means of the nonparametric Wilcoxon rank test stratified by its baseline values with two-sided α -level of 5%. Two adaptive interim analyses after 32 and 80 patients are planned according to the Pocock adjusted levels $\alpha_p = 0.0221$. The results of the sequential groups are combined by the inverse-normal-method (Lehmacher, Wassmer, 1999). There are no prespecified futility margins, but the DSMB can stop the study in the case of insufficient interim results.

Furthermore, 95% confidence intervals will be determined, and the results will be presented graphically by means of box-and-whisker plots.

The analyses will be carried out by the trial biostatistician.

11.4.3 Secondary Analyses

The secondary endpoints are time to improvement of at least 2 points on the WHO Ordinal Scale, the proportion of subjects with ARDS (defined by Berlin severity criteria) within 14 days after enrollment and the proportion of participants alive and not having required invasive or non-invasive ventilation at 14 days after enrollment. They will be tested only after a significant test of the primary endpoint (a priori ordered hypotheses), therefore, no alpha adjustment is necessary.

Quantitative secondary study parameters will be described based on their mean, standard deviation, median, IQR, minimums and maximums and portrayed by Kaplan-Meier plots and compared with the Wilcoxon rank test.

Qualitative secondary study parameters will be analyzed by means of absolute and relative frequencies. Pairwise Chi-Square tests will be carried out in order to compare each of the active treatments to placebo. Moreover, 95% confidence intervals for the treatment differences will be calculated.

Other outcomes of interest will be analyzed by means of descriptive and exploratory statistics.

The analyses will be carried out by the trial biostatistician.

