11.4.4 Interim Analyses

Two interim analyses after 32 and 80 patients are planned according to the Pocock adjusted levels $\alpha_p = 0.0221$. Based on the results of an interim analysis the sample size can be adjusted (Lehmacher, Wassmer, 1999). There are no prespecified futility margins, but the DSMB can recommend stopping the study in the case of insufficient interim results.

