14.5 Efficacy

Continuous variables will be summarized using the mean, standard deviation, median, minimum, maximum values. Categorical variables will be summarized using the cell frequencies and percentage of patients in each category.

All statistical tests performed will be two-tailed with significance determined by reference to the 5 % significance level, unless otherwise stated. The null hypothesis at all times will be the equality of the treatments being compared.

Furthermore, the results will be presented graphically.

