14.8 Multiplicity

Pocock's group sequential approach is used and the significance levels in the interim analysis are adjusted for the primary variable accordingly ($\alpha_p = 0.0221$).

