14.10 Interim Analysis

Two interim analyses after 40 and 80 patients are planned according to the Pocock adjusted levels $\alpha_p = 0.0221$. Based on the results of an interim analysis the sample size can be adjusted (Lehmacher, Wassmer, 1999). There are no prespecified futility margins, but the DSMB can recommend stopping the study in the case of insufficient interim results.

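### Testing secondaries only after a significant primary does not by itself justify the full 5% level, because the primary can cross at three looks and the timing of the secondary tests is not fixed

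*Protocol*

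**What the plan says.** Protocol 11.4.3 and SAP 14.5.2 name three secondary endpoints for testing: time to a 2-point improvement on the WHO scale, ARDS within 14 days, and being alive without ventilation at 14 days. Both then say: "They will be tested only after a significant test of the primary endpoint (a priori ordered hypotheses), therefore, no alpha adjustment is necessary".

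The level comes from SAP 14.5: "All statistical tests performed will be two-tailed with significance determined by reference to the 5 % significance level, unless otherwise stated". Nothing else is stated for the secondaries. SAP 14.8 limits the sequential correction to the primary: "the significance levels in the interim analysis are adjusted for the primary variable accordingly".

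The primary is tested up to three times. Protocol 11.4.4 says "Two interim analyses after 32 and 80 patients are planned"; SAP 14.10 says "Two interim analyses after 40 and 80 patients are planned". Each look uses a two-sided level of 0.0221, and the final analysis is at about 120 patients. For the primary, Protocol 11.4.2 adds: "The results of the sequential groups are combined by the inverse-normal-method". Neither document gives the secondaries a boundary, a combination rule or a fixed analysis time.

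**The concern.** A gate on the primary protects a secondary at full alpha when there is one analysis time, because the secondary then has one chance to be falsely significant. With three looks, the gate opens at a time chosen by the data. If the two endpoints are positively correlated, it tends to open when the secondary is also high by chance, and that value is then compared with 1.96.

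The documents give no correlation. A substantial one is plausible: time to improvement is read from the same WHO scale as the primary, and ventilation and death are among its upper categories. At stake is a claim of benefit on a secondary endpoint with a higher chance of being false than its nominal level, under a plan that says explicitly that no correction is needed.

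**Working it through.** **Inputs from the documents.** Looks at 32/80/120 (protocol) or 40/80/120 (SAP); primary level 0.0221 two-sided per look; secondary level 5% two-sided; effect 1 point, SD 1.5, allocation 80 + 40 (Protocol 11.2).

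**Assumptions.** Primary-secondary correlation ρ, shown from 0 to 1. Inverse-normal weights proportional to sample size, because the plan states none. The secondary is tested at the look where the primary first crosses.

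**1. The plan's own figure.** For three equally spaced looks and an overall two-sided 5%, numerical integration gives a Pocock level of 0.02205, so 0.0221 reproduces. The critical value is Φ⁻¹(1 − 0.0221/2) = 2.289. At 32/80/120, 0.0221 gives an overall 5.16% for the primary; the level for exactly 5% is 0.0214 (critical value 2.30).

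**2. Quantity of interest.** With the secondary null true,

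false-benefit rate = Σₖ P(no primary crossing before look k, Zₖ(primary) > 2.289, Zₖ(secondary) > 1.96), k = 1, 2, 3,

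maximised over the primary drift θ, the expected final primary z-value. The nominal value is 2.5%.

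**3. Worst case over θ.** Simulation with 1 to 2 million paths; numerical integration at ρ = 1:

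| ρ | 40/80/120 | 32/80/120 |
|---|---|---|
| 0 | 2.5% | 2.5% |
| 0.5 | 2.9% | 3.0% |
| 0.7 | 3.3% | 3.4% |
| 0.8 | 3.5% | 3.7% |
| 0.9 | 3.9% | 4.1% |
| 1.0 | 5.2% | 5.2–5.3% |

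At ρ = 1 the maximum occurs at a drift of only 0.55 to 0.65. At ρ = 0.5 to 0.9 the worst case is 1.2 to 1.6 times nominal (2.9/2.5 to 4.1/2.5).

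**4. At the design effect.** θ = (1/1.5) × √(80 × 40/120) = 0.667 × 5.164 = 3.44. For ρ from 0.3 to 1 the rate is 2.6% to 2.9% (40/80/120) or 2.8% to 3.1% (32/80/120).

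**5. Both tails.** Counting a false secondary result in either direction after a significant primary in either direction, the total does not exceed 5% up to ρ = 0.95. At ρ = 1 it peaks at 6.0% (40/80/120) and 6.1% (32/80/120).

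**6. After correction.** With the secondary tested at 0.0221 at the crossing look, the maximum false-benefit rate is 2.51% for equally spaced looks and 2.58% for 32/80/120. Using 0.0214 for both endpoints at 32/80/120 brings it back to 2.5%.

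**The case against.** - **Timing is inferred.** Neither document says that the secondaries are tested at the look where the primary crosses. SAP section 1 describes evaluations for the final statistical analysis, and Protocol 2.7 makes stopping for early benefit an option, not a consequence of crossing. If the secondaries are tested once, at a final analysis whose time is fixed, there is no inflation. This stands. But no text commits to that, and Protocol 11.2's statement that primary and main secondary endpoints are analysed at latest 14 days after start of treatment reads as a time in each patient's follow-up, not as a choice of look.
- **The yardstick.** SAP 14.5 sets two-sided 5% and no separate 2.5% limit. Against 5% in total, the plan holds for correlations up to 0.95. This also stands. The one-sided count is a stricter standard, used here because the hypothesis in Protocol 11.1 is directional and only a benefit claim would matter.
- **Doubling.** A reader might infer that the false-benefit error doubles. That needs a correlation of 1, a small primary effect and a true-null secondary together, and none of the listed secondaries is a perfect copy of the day-7 score. The documents do not support it as the expected size.
- **Study phase.** This is an exploratory phase 2a pilot, which limits the consequences. The plan nevertheless makes a formal claim about error control.

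**Conclusion.** The stated reason does not support the stated conclusion. A gate that can open at any of three looks does not protect a secondary tested at the full 5% unless its analysis time is fixed, and the documents leave that open.

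The size is modest. If testing occurs at the crossing look, the excess over 2.5% in the worst case is about 0.5 to 1.2 percentage points at assumed correlations of 0.5 to 0.8, and about 0.1 to 0.6 points near the design effect. The figure of about 5.2% is a ceiling, and so is 6.1% for both tails. The conclusion holds under either look schedule. The sizes rest on the assumed correlation, sample-size weights and the reading of the timing. It would be wrong to conclude that the plan's two-sided 5% is broken in general.

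The same sentence has a further gap: it calls the hypotheses ordered without giving an order. The lists do not supply one, since Protocol 4.3 puts ventilation-free survival before ARDS and 11.4.3 reverses them. If all three were tested at 5% once the gate is open, with all nulls true and tests independent, the chance of at least one false result would be 1 − 0.95³ = 14.3%.

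**What to change.** In Protocol 11.4.3 and SAP 14.5.2, delete the statement that no adjustment is needed and replace it with one of two rules:

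1. Test the secondaries at the look where the primary is rejected, with the same inverse-normal combination and the same per-look Pocock level as the primary. That is 0.0221 for equally spaced looks, or about 0.0214 for both endpoints if the looks are 32/80/120 with sample-size weights.
2. Name in advance one fixed analysis time for the secondaries, whichever look the primary crosses at.

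State the order of the three secondaries and that testing stops at the first non-significant one. Reconcile the first look (32 or 40) and state the combination weights, since the level depends on both.

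The cost is protocol and SAP wording. Option 1 also loses a little secondary power (critical value about 2.29 to 2.30 instead of 1.96). No change to data collection or planned sample size is needed.
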